## **3.8 Open-Label Period**

Open-label period is defined as the time from the first dose of open-label study drug to the last study visit if the subject is enrolled into open-label extension period of the study.

## 4.2 Missing Data

For the primary endpoint and key secondary efficacy endpoints, missing data will not be imputed in the primary analyses. A supportive sensitivity analysis for the Month 12 LVEF endpoint will be conducted where missing LVEF values at Month 12 will be imputed using Month 6 values, if available. Subjects missing LVEF at both Month 6 and Month 12 will be excluded from this supportive analysis. For long-term analyses in the open-label extension, subjects missing data at key timepoints (Month 24, Month 36) will be excluded from the respective analyses. No other imputation will be provided for any endpoint.

Since LVEF is a key efficacy endpoint, the pattern of missing data will be carefully evaluated to assess potential bias. The frequency and reasons for missing LVEF measurements will be

summarized by treatment group to determine whether missingness might be related to treatment or disease progression. If systematic differences in missing data patterns are identified between treatment groups, additional sensitivity analyses may be conducted using multiple imputation methods that account for the potential relationship between the likelihood of missing data and the unobserved outcomes. This would involve creating multiple complete datasets based on observed covariates and outcomes, analyzing each dataset, and combining results according to Rubin's rules. These additional analyses would be considered exploratory and would be used to evaluate the robustness of the primary analysis approach.

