### 6.2.1 Change from baseline in LVEF and Myocardial Strain using CMR

The secondary analysis will focus on the change from baseline in LVEF and myocardial strain over 12 months of dosing.

The change from baseline in LVEF and myocardial strain will be compared between the treatment groups (High-Dose Ifetroban vs Placebo; Low-Dose Ifetroban vs Placebo) using Wilcoxon rank sum test for ITT population.

The number and change from baseline in LVEF and myocardial strain for each treatment group and overall, in the ITT population will be summarized descriptively. The following myocardial strain endpoints will be summarized:

- Indexed left ventricular end diastolic volume (LVEDVi)
  - LVEDVi = LVEDV/body surface area (BSA)
  - BSA calculation from CMR dataset using the Haycock method for pediatrics =  $0.024265 \times (\text{ht\_cmr})^{0.3964} \times (\text{wt\_cmr})^{0.5378}$
  - From CMR dataset: LVEDVi = “lvedv\_cmr”/ “bsa\_calc\_cmr”
- Indexed left ventricular end systolic volume (LVESVi)
  - LVESVi = LVESV/body surface area
  - BSA calculation from CMR dataset using the Haycock method for pediatrics =  $0.024265 \times (\text{ht\_cmr})^{0.3964} \times (\text{wt\_cmr})^{0.5378}$
  - From CMR dataset: LVESVi = “lvesv\_cmr”/ “bsa\_calc\_cmr”
- Mid Ecc (circumferential strain)

- Global Ecc
- Late gadolinium enhancement, full-width half-maximum (LGE FWHM)
- Number of segments with LGE (number of LGE segments with values >0)
- Base T1
- Mid T1

A subject data listing of all LVEF and myocardial strain will be provided.

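### SAP 4.2 describes its exploratory multiple imputation as covering missingness that depends on unobserved LVEF, but the procedure it gives is imputation under missing at random, and the quantity to be pooled is not named

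*SAP*

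**What the plan says.** SAP 4.2 (Missing Data) leaves missing values unimputed in the primary analyses. One supportive analysis fills missing Month 12 LVEF with the Month 6 value. The section then states "No other imputation will be provided for any endpoint".

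The next paragraph plans a summary by arm of how often, and why, LVEF is missing, and continues: "If systematic differences in missing data patterns are identified between treatment groups, additional sensitivity analyses may be conducted". The method offered is "multiple imputation methods that account for the potential relationship between the likelihood of missing data and the unobserved outcomes". The procedure is then given: "This would involve creating multiple complete datasets based on observed covariates and outcomes", with each dataset analysed and the results combined by Rubin's rules. On status and purpose: "These additional analyses would be considered exploratory and would be used to evaluate the robustness of the primary analysis approach".

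SAP 6.2.1 compares each dose with placebo on LVEF change "using Wilcoxon rank sum test for ITT population".

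Two other places bear on imputation. SAP 3.3 (Study Endpoints) says that subjects who stop treatment before week 52 have their data carried forward by LOCF. Protocol 11.7 allows no imputation except the Month 6 substitution.

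**The concern.** The aim and the method, in adjacent sentences, do not match. A relation between the chance of being missing and the unobserved value, over and above what the observed data explain, is MNAR. Imputing from observed covariates and outcomes assumes that no such residual relation exists. An analysis that makes that assumption cannot show what happens when it fails.

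LVEF is the endpoint on which the sample size rests, and missing data are expected: planned dropout is 25% in Protocol 11.1 and 10% in SAP 3.4. In a progressive cardiomyopathy it is plausible that subjects without a Month 12 scan differ in outcome from those with one. The Month 6 substitution assumes no change over the second six months, and the Month 6 CMR is itself optional (Protocol 8.1.2). This imputation paragraph is therefore the only place where the SAP claims to deal with outcome-dependent missing LVEF.

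Rubin's rules need an estimate and its variance from each completed dataset. A Wilcoxon p-value is neither, and SAP 4.2 does not say what takes its place.

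**Working it through.** **1. The plan's own figures.** The documents give no figure for the imputation. The nearest are the power statements in SAP 3.4 (8 per arm within stage, effect size 1.6 SD, two-sided 0.05).
- t-test: noncentrality 1.6 × √(8/2) = 3.2 on 14 df gives power 84.5%, against a stated figure of more than 85%.
- Wilcoxon: 40,000 simulated trials with the exact rejection region give 82.3%, against a stated figure of more than 80%.

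These agree to within about half a point and are not in dispute here.

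**2. Aim against procedure (SAP 4.2).**

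| Element | What SAP 4.2 gives |
|---|---|
| Aim | A link between missingness and unobserved outcomes (MNAR) |
| Imputation inputs | Observed covariates and outcomes |
| Delta, pattern-mixture, reference-based or selection component | None |
| Sensitivity parameter | None |
| Imputation model, number of imputations | Not stated |
| Estimate and variance pooled | Not stated |
| Criterion for a systematic difference | Not stated |

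The SAP does not use the term MAR. That reading follows from the second row together with the third.

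**3. What MAR imputation leaves behind.** Let f be the fraction missing in an arm, and δ the amount by which the missing values are truly worse than MAR predicts. After MAR imputation the arm mean is too favourable by f × δ, so the between-arm error is the difference in f × δ.

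- Departure in one arm only, δ = 0.5 to 1.5 SD (assumed). At 10% missing: 0.10 × 0.5 to 0.10 × 1.5 = 0.05 to 0.15 SD. At 25% missing: 0.25 × 0.5 to 0.25 × 1.5 = 0.125 to 0.375 SD. The largest of these is 0.375/1.6 = 23% of the design effect.
- In LVEF points, with 25% of placebo and 10% of high-dose subjects missing and δ = 3, 5 or 8 points (all assumed): (0.25 − 0.10) × δ = 0.45, 0.75 or 1.2 points. Here the placebo mean is flattered more, so the bias runs against ifetroban. Exchanging the two fractions reverses the sign. The documents give no LVEF SD in points, so these values cannot be compared with the design effect of 1.6 SD.

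**4. Simulation (all inputs assumed).** There is no true effect and the baseline–outcome correlation is 0.6. Worse outcomes are more likely to be missing in the active arm only. Imputation is by Bayesian normal regression on baseline and arm.

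| Setting | Missing, active / control | Complete-case bias | Bias after MAR imputation | Share left |
|---|---|---|---|---|
| 2,000 per arm | 28.5% / 24.9% | +0.233 SD | +0.154 SD | 0.154/0.233 = 66% |
| 16 per arm, stronger dependence | 31.3% / 24.9% | +0.358 SD | +0.243 SD | 0.243/0.358 = 68% |

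In this scenario the bias favours the active arm. At 16 per arm the type I error after MAR imputation was 10.0% for the mean difference, 8.8% for a pooled rank-sum z and 8.0% for a pooled Hodges-Lehmann shift, against a nominal 5%.

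**5. Can rank-based results be pooled?** Rubin's total variance is T = W + (1 + 1/M)B, where W is the mean within-dataset variance, B the between-dataset variance and M the number of imputations. Two inputs were tried at 16 per arm with about 25% missing completely at random: the standardized rank-sum z with W = 1, and the Hodges-Lehmann shift with an SE taken from its confidence interval. Type I error was 4.3% and 4.4%. Pooling is feasible once the quantity is named.

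**The case against.** The strongest defence is that the aim can be read charitably. Under MAR, missingness may still be associated with the unobserved value, provided the observed data explain the association. On that reading the two sentences agree. If that is the intention, the section should say so. The imputation would still not examine any remaining dependence, which is what a robustness check on informative dropout has to do.

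It is also fair to say that the analysis is optional and exploratory, that LVEF is a secondary endpoint, and that no planned conclusion depends on this paragraph. That limits the severity. Comparing complete-case with MAR results is a legitimate check in itself.

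Four stronger readings are tempting, and the documents do not support them.
- *Rubin's rules cannot be used with a Wilcoxon analysis.* They can, as step 5 shows. The gap is one of specification.
- *The imputation achieves nothing under MNAR.* Relative to complete cases it removed about a third of the bias in both simulated settings.
- *Wilcoxon is the only LVEF analysis planned.* SAP 6.4.2 plans mixed models for key efficacy parameters, and SAP 14.3.8 plans covariate adjustment against the natural history cohort. SAP 4.2 does not say which analysis is applied to each completed dataset.
- *The trigger would rarely fire.* SAP 4.2 sets no significance test. It has the frequency and reasons for missingness reviewed by arm, so the power of a formal test says nothing about how often the trigger would be met. What can be said is that no criterion is given.

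**Conclusion.** The point holds in a limited form. SAP 4.2 attributes to its multiple imputation a property that the stated procedure lacks, and leaves the pooled quantity undefined. The conclusion about the method follows from the text alone. The sizes do not: the residual biases of 0.15 and 0.24 SD, the type I error of 8–10% and the range of 0.45–1.2 LVEF points rest on the assumptions in steps 3 and 4. A stronger observed predictor, such as Month 6 LVEF where it was obtained, would leave less.

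The direction is not fixed either. The simulated scenario favours ifetroban, while the scenario in LVEF points runs against it. A reader might infer that the plan is tilted towards a false positive, or that the report will overclaim. Neither can be concluded from the documents. This should be corrected before the analysis, but it does not threaten the primary safety endpoint.

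**What to change.** 1. Keep the summary of the frequency and reasons for missing LVEF by arm.
2. Relabel the existing analysis as multiple imputation under MAR, and state the imputation model and number of imputations. Name what is pooled: for example, the ANCOVA treatment difference in Month 12 LVEF change adjusted for baseline LVEF, with its SE, or the Hodges-Lehmann shift with its SE.
3. Add a delta-adjusted tipping-point analysis that shifts imputed Month 12 LVEF by arm over a stated range (for example 0 to −10 points) and reports where the conclusion changes. Run it whether or not missingness patterns look different, and describe only this analysis as addressing unobserved outcomes.
4. Reconcile the paragraph with the sentence in SAP 4.2 that rules out other imputation, with the LOCF statement in SAP 3.3, and with Protocol 11.7. Record any departure from the protocol in SAP 8, which at present lists none.

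The cost is SAP wording and a standard multiple-imputation program. No new data are needed.

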### **4.3 Interim Analysis**

An early analysis was performed when half the target enrollment has completed the six months visit and assessments. Key findings from the interim analysis were summarized and distributed to limited personnel. To maintain study integrity with respect to subsequent treatment visits, the team that will perform the early analysis and all related activities were external and restricted from participating in data review or decisions following the early analysis but may participate in the analysis following final database lock.

### **4.4 Data Definitions and Analysis Issues**

#### **4.4.1 Baseline Definition**

The baseline measurement for the DB period and the OL period is defined as the last non-missing measurement prior to or on initiation of ifetroban; unless otherwise specified, the baseline value for all endpoints will be the non-missing value. If the time of the assessment or measurement was not recorded and it occurred on the same day that the first dose of drug started, it will be assumed to be taken before the study drug.

Change from baseline will be calculated as follows for the purposes of calculating summary statistics for the outcome measures:

Change from baseline = post-baseline value – baseline value

#### **4.4.2 Treatments**

The following treatments will be given in the DB period:

- High Dose Ifetroban
- Low Dose Ifetroban
- Placebo

- Placebo group created from the Natural History dataset (see [Section 4.5](#))
- Overall

The following treatments will be given in the OL period:

- High Dose Ifetroban

#### **4.4.3 Multicenter Studies**

The centers will be pooled for analysis.

#### **4.4.4 Multiple Comparisons/Multiplicity**

Multiplicity and multiple comparisons do not apply to these secondary and exploratory objectives. No adjustments will be made for multiple comparisons or multiplicity. Changes to Protocol Specified Analysis

There are no changes to the protocol specified analyses.

### **4.5 Natural History Study Comparisons**

Natural history study (NHS) data will be incorporated into analyses to supplement the placebo group and serve as a comparator for open-label extension periods.

#### **4.5.1 Propensity Score Matching Methodology**

Propensity scores will be calculated separately for the DB and open-label periods using logistic regression models with treatment assignment as the dependent variable. The independent variables will include: age, baseline LVEF, background DMD medications (steroids, ASO/exon-skipping therapy), and cardiac medications (ACEi, ARB, ARNI, beta-blocker, calcium channel blocker, aldosterone receptor antagonist, diuretic) as defined in [Section 14.3.4](#).

#### **4.5.2 Matching Algorithm**

For the DB period, NHS subjects will be matched to high-dose ifetroban subjects at a 2:1 ratio using a global optimal algorithm based on the nearest neighbor approach without replacement and without caliper. For the open-label period, NHS subjects will be matched to all open-label subjects at a 2:1 ratio using the same methodology.

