Sample Size: The sample size is based on the comparison of each dose level of ifetroban (Low Dose or High Dose) to placebo with respect to change from baseline in LVEF using CMR for each disease stage, early (LVEF > 45%) or advanced (current/historical LVEF 35% - 45%). Assuming observations from each treatment group have normal distributions with an effect size of 1.6 for the comparison of a dose of ifetroban to placebo, 8 subjects for each treatment group within disease stage will provide power exceeding 85% for a t-test at two-sided level 0.05. Under these assumptions, 8 subjects for each treatment group within disease stage will provide power exceeding 80% for the Wilcoxon rank sum test at two-sided level 0.05. A total of 48 DMD subjects will be enrolled: 24 subjects with early stage DMD (LVEF > 45%) and 24 with advance stage DMD (current/historical LVEF 35%-45%). Assuming a dropout rate of 25%, 60 subjects will be recruited to meet the target sample size of 48 subjects.		

Name of Sponsor:	Name of Finished Product:	Name of Active Ingredient:
Cumberland Pharmaceuticals	Ifetroban Capsules	ifetroban
Enrollment:		
Subjects will be randomly assigned to one of three oral treatment groups: low-dose ifetroban, high-dose ifetroban or placebo for 12 months based on weight within each disease stage, early (LVEF > 45%) or advance (current/historical LVEF 35%-45%).		
Low Dose: < 35 kg: 50 mg, ≥ 35 kg: 100 mg/day		
High Dose: < 35 kg: 150 mg, ≥ 35 kg: 300 mg/day		
Analysis Population:		
All subjects who receive at least one dose of study medication will be included in the Safety Population. All safety data will be summarized for subjects in the Safety Population.		
The Intent-To-Treat (ITT) Population will consist of all treated subjects with at least one post-baseline assessment. The Per Protocol (PP) Population will consist of all subjects in the ITT population with no major protocol violations, including violation of inclusion or exclusion criteria or insufficient dosing where the latter includes missing more than 2 consecutive weeks of dosing for any reason or missing >20% of prescribed doses between visits. Summary statistics will be presented for both the ITT and PP Populations.		
Interim Analysis:		
An early analysis will be performed when half the target enrollment has completed the six month visit and assessments. Key findings for the interim analysis will be summarized.		
Historical Comparator Analyses:		

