7.3.1 Inclusion Criteria

Individuals who meet all of the following criteria are eligible for enrollment as study subjects:

1. Males 7 years of age and older with the diagnosis of DMD, defined as phenotype consistent with DMD and either positive genotype, first degree relative with positive genotype, or confirmatory muscle biopsy.
2. Stable dose of oral corticosteroids for at least 8 weeks or has not received corticosteroids for at least 30 days.
3. Stable cardiac function defined as change in LVEF of < 15% and no heart failure admission over the last 12 months; LVEF 35% or greater by cine CMR or echocardiography; myocardial damage in one or more left ventricular segments evident by late gadolinium enhancement allowed; concurrent angiotensin-converting enzyme inhibitors (ACEI), beta-blocker (BB) or angiotensin receptor blocker (ARB) therapy allowed (selection of which dictated by clinical care) if started three months or greater from first dose of IMP without change in dose. Aldosterone receptor antagonists (e.g. spironolactone or eplerenone) allowed if started 12 months or greater from first dose of IMP. No changes throughout the study allowed except in the event of a decline in left

ventricular ejection fraction (LVEF) >5% following the baseline CMR as measured by a subsequent CMR at the same center. Should this occur, changes in cardiac medications are allowed on study, and the patient may remain on IMP.

- a. **Late-stage cohort:** Subjects are eligible for the late-stage cohort if the subject has:
 - i. LVEF 35%-45% by cine cardiac magnetic resonance imaging (MRI) or echocardiography or
 - ii. historically documented LVEF 35%-45% by cine cardiac magnetic resonance imaging (MRI) or echocardiography and if their baseline MRI is less than 50%.
4. Subjects aged 18 years and older, informed consent obtained directly. For subjects ages 7–17 years old (yo), both assent from the subject and permission from a parent or guardian.
5. AAV-based gene therapy permitted if ≥ 2 years from AAV administration and subject has documented cardiac decline defined as >5% decline in LVEF over a 2-year period following AAV administration using consecutive CMRs or echocardiography performed at the same center (must still meet inclusion criterion #3).

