#### 3.1 Study Design

This is a double-blind (DB), placebo-controlled, multicenter, dose-ranging study with an open-label extension (OL) to determine the safety, pharmacokinetics, and efficacy of two dose ranges of oral ifetroban in subjects with DMD.

[figure not shown]
Subjects who meet eligibility criteria will be randomly assigned to one of three treatment groups 1:1:1 ratio, low-dose ifetroban, high-dose ifetroban or placebo, and dosed based on weight. Each treatment group will be evaluated by eight subjects with early stage (LVEF >45%) and eight subjects with advance stage (LVEF 35% - 45%) DMD for at least six months and a maximum of 12 months. Subjects who complete 12 months of treatment will be eligible to participate in an OL extension ([Figure 1](#)).

All subjects who receive IMP will be assessed for safety. All subjects with at least one efficacy assessment post-baseline will be evaluated for efficacy. Blood and urine will be collected for standard and novel cardiac biomarkers.

The clinical study will be conducted with two periods:

- Screening period of up to 12 weeks.
- Randomized ifetroban/placebo treatment period of 12 months.
- Subjects who complete 12 months of treatment will be eligible to participate in an OL extension.

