#### **14.3.4 List of Baseline Covariates for Modeling**

The following baseline covariates will be included in the DB and OL Model to create the propensity score.

- Age
- Baseline left ventricular ejection fraction (LVEF). Baseline will represent pre-treatment values in DB and Month 12 visit values will be the baseline in the OL study.
- Background DMD medications (current steroids, Current ASO/exon skipping)
- Additional cardiac medications (Aldosterone antagonists, Beta-blocker, ACEi, ARB, Calcium channel blockers, ARNI)

The following chart will be used to define the baseline med covariates in the NH dataset.

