#### **14.3.6 Analysis Population**

For the DB period, only high dose active and placebo subjects with Month 12 evaluable cardiac efficacy data will be included in the analysis.

For OL, all ifetroban treated subjects in the ITT population will be matched with natural history data.

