#### 14.3.8 Sensitivity Analysis

A sensitivity analysis will be performed for the DB period, by re-selecting natural history subjects (Placebo:High-Dose ifetroban) using the average Treatment Effect (ATE), by applying the inverse probability of treatment weighting (IPTW). These weights will create pseudo-population of the untreated, which has the same covariate distribution as the treated. While every treated subject received a weight of  $[1/PS]$ , every untreated subject is weighted by  $[1/(1-PS)]$ . An additional exact matching analysis will be explored for feasible categorical variables.

Two separate sensitivity analyses will be performed using caliper 0.2 and using exact matching.

An additional sensitivity analysis will be performed comparing the ifetroban treatment groups to the entire eligible NH cohort (before matching) to evaluate the robustness of findings from the matched analysis. This will help assess whether the treatment effect observed in the matched comparison remains consistent when compared against the broader NH population. This analysis will use appropriate covariate adjustment in the statistical models to account for baseline differences between groups rather than relying solely on matched pairs.

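### The main double-blind matching to natural history controls does not hold disease stage fixed, so the control group may contain fewer advanced-stage subjects than the half-advanced high-dose arm

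*SAP*

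**What the plan says.** SAP 3.1 plans equal halves: "Each treatment group will be evaluated by eight subjects with early stage (LVEF >45%) and eight subjects with advance stage" disease. The Protocol synopsis (Enrollment) assigns subjects to "low-dose ifetroban, high-dose ifetroban or placebo for 12 months based on weight within each disease stage", and SAP 3.4 sizes the trial within stage. Advanced stage is not purely a baseline measurement. Protocol 7.3.1 also admits a subject with a past LVEF of 35-45% "and if their baseline MRI is less than 50" percent.

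For the double-blind NHS comparison, SAP 4.5.2 states: "NHS subjects will be matched to high-dose ifetroban subjects at a 2:1 ratio using a global optimal algorithm". Each control is used once and no caliper applies; SAP 14.3.1 repeats this. On the score, SAP 4.5.1 says "The independent variables will include: age, baseline LVEF, background DMD medications (steroids, ASO/exon-skipping therapy), and cardiac medications" in seven classes, which makes 11 terms. SAP 14.3.4 lists "Additional cardiac medications (Aldosterone antagonists, Beta-blocker, ACEi, ARB, Calcium channel blockers, ARNI" and leaves out diuretics, which makes 10. Baseline LVEF is on both lists and stage is on neither.

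Under SAP 14.3.6, "only high dose active and placebo subjects with Month 12 evaluable cardiac efficacy data will be included in the analysis". Groups are compared by an unadjusted Wilcoxon rank sum test, and SAP 4.5.3 labels the result supplementary. SAP 14.3.8 plans sensitivity analyses by IPTW, a 0.2 caliper, exact matching, and a covariate-adjusted comparison with the whole eligible NHS cohort. On exact matching it says "An additional exact matching analysis will be explored for feasible categorical variables", and it names no variable. SAP 14.3.7 tabulates baseline LVEF and propensity score by group, but no stage-balance criterion is set.

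**The concern.** The half-and-half mix is imposed by the design, and nothing suggests that the NHS shares it. A single score trades LVEF off against nine or ten other terms, so two subjects can have the same score and lie in different LVEF bands. With 16 high-dose subjects there are 16/11 = 1.5 treated subjects per term (12/11 = 1.1 if a quarter are lost), so the coefficients are poorly determined.

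The planned test compares change in LVEF between whole groups without adjustment. If one-year change depends on stage, a control group with another stage mix would shift the comparison for reasons unrelated to treatment, and the test would not correct for it.

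**Working it through.** **The plan's own figures.** The documents give no stage mix for the matched controls. The only related figure is power within stage (SAP 3.4): n = 8 per group, effect size 1.6, two-sided 0.05. The noncentrality is 1.6 x sqrt(8/2) = 3.2 on 14 degrees of freedom. This gives 84.5% for the t-test (stated as above 85%). Simulation gives 82.4% for the Wilcoxon test (stated as above 80%). The figures agree to within half a point and show that stage is the level at which the trial was sized.

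**What 2:1 matching needs.** There are 16 high-dose subjects, hence 2 x 16 = 32 NHS controls. A 50% advanced share needs 2 x 8 = 16 advanced NHS controls. If the eligible pool holds only A advanced subjects, the share cannot exceed A/32. With A = 10 the ceiling is 10/32 = 31%, whatever the algorithm.

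**Simulation of the planned matching.** Inputs from the documents: 8 early and 8 advanced high-dose subjects, the 11 terms of SAP 4.5.1, a logistic score, and optimal 2:1 assignment without replacement or caliper. Assumptions not in the documents: eligible pool of 60-400, 10-50% of it at LVEF 35-45%, early-stage LVEF about 57 (SD 5.5), and plausible drug-use rates. There were 300 runs per setting. The pooled column adds 16 placebo subjects split 8/8: (32 x share + 8)/48.

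| Pool; % advanced | Matches crossing stage | Advanced among NHS controls | Pooled with placebo | Advanced with 0.2 caliper | Advanced with exact stage match |
|---|---|---|---|---|---|
| 100; 10% | 37% | 24% | 33% | 23% | 30% |
| 100; 20% | 36% | 37% | 41% | 36% | 49% |
| 200; 10% | 29% | 34% | 39% | 32% | 49% |
| 200; 20% | 32% | 42% | 45% | 40% | 50% |
| 200; 30% | 40% | 46% | 47% | 45% | 50% |
| 200; 50% | 48% | 51% | 51% | 51% | 50% |
| 400; 10% | 25% | 40% | 43% | 37% | 50% |

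Across all settings about 25-48% of matches cross stage, and 15-51% of matched controls are advanced. The low end, 15%, comes from the smallest pools with 10% advanced; pooled it becomes (32 x 0.15 + 8)/48 = 27%. These are averages. A single matching varies by about 12-15 points either way (31-59% for a pool of 200 with 30% advanced).

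**Other settings.** A different LVEF shape (pool 100-250, mean 52-55, SD 9) gave 37-40% crossing and 28-36% advanced. If three of the eight advanced high-dose subjects entered by historical LVEF, crossing was 33-47%. A score with only age and LVEF lowered crossing to 9-39%, so the many drug terms contribute. A 0.2 caliper left 25-49% crossing.

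**A lower ratio in the scarce band.** With 1:1 in the 35-45% band and 2:1 above it, there are 8 advanced and 16 early NHS controls: 8/24 = 33%. Adding placebo gives 16/40 = 40%. A lower ratio therefore needs stratification or weights. Weighting the 16 advanced controls by 24/16 = 1.5 makes the bands equal, 24 to 24.

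**The case against.** The strongest reply is that baseline LVEF, the variable behind stage, is already in the score. The NHS result is supplementary beside a randomised comparison, the placebo arm pulls the pooled mix towards 50%, and four sensitivity analyses are planned. Much of this stands, and it limits the weight of the point. It does not remove it. LVEF as one term among 10 or 11 does not fix the stage mix, none of the sensitivity analyses names stage, and the caliper barely changes the advanced share.

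A reader might go further in four ways that the documents do not support.

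- That the control group will certainly have another stage mix. The NHS pool is not described, and in some plausible pools the average mix is balanced.
- That cross-stage pairs bias the test. The Wilcoxon test is unpaired, so who was matched to whom does not enter it. In the simulation, crossing is highest (46-48%) where half the pool is advanced, and there the mix is balanced.
- That the missing caliper is the cause. Adding one leaves crossing and mix about where they were.
- That advanced-stage subjects would be set against healthier controls in stage-specific NHS results. SAP 14.3.7 lists no stage split for the double-blind NHS tables. If the subgroups of SAP 6.5 were applied, controls would be classified by their own LVEF.

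**Conclusion.** The point holds as a risk in a supplementary analysis. The main matching has no stage constraint although stage is the trial's own stratum. Depending on the pool, matched controls may be anywhere from about 15% to 51% advanced against 50% in the high-dose arm, or about 27% to 51% after pooling with placebo. The shortfall is clear when advanced NHS subjects are scarce, and small or absent on average when about 30% or more of a pool of 200 is advanced.

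These ranges rest on assumed pool sizes, LVEF distributions and drug-use rates, and on a full high-dose arm of 8 and 8. The resulting bias in LVEF change was not computed, because the documents give no rate of change by stage; neither its size nor its direction can be stated. The calculations do not cover the open-label matching.

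**What to change.** In SAP 4.5.2 and 14.3.1:

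- Make baseline LVEF band (35-45% v >45%, measured the same way in both sources) an exact-match variable in the main double-blind matching, and include it in the score model.
- Report separately the subjects who entered the advanced cohort by historical LVEF, because some may fall in the upper band at baseline.
- Compare groups with a Wilcoxon test stratified by band, or with weights that restore the high-dose stage mix. If the 35-45% band holds fewer than two eligible NHS controls per high-dose subject, a lower ratio there then does not bring the imbalance back.
- Keep the present matching as a sensitivity analysis, and state whether the score has 10 or 11 terms.

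The cost is SAP wording and one matching option. The downsides are fewer controls in the 35-45% band if the NHS has few such subjects, and slightly looser balance on minor drug classes. In the simulation, exact matching gave 49-50% advanced controls once the pool held about 16 or more advanced subjects.
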